Director, Viral Hepatitis Center
Medical Director, Liver Transplantation
University of Pennsylvania
[name]
[contact]
[contact]

INFUSE: Summary of VERSION 4 Dated: June 29, 2021 Changes

Section: SYNOPSIS

- Expansion of inclusion criteria to include patients that are not liver transplant eligible or listed for liver transplantation
- Modification of inclusion criteria
- Modification of exclusion criteria to exclude patients 1) MELD ≥ 35 2) Advanced HCC with expected survival of < 6 months

Section: SAFETY AND EFFICACY ASSESSMENTS

- Clarification of secondary efficacy endpoint for Serum creatinine and incidence of dialysis at Day 30, Day 90, Day 180, and Day 365 after liver transplantation and those alive without transplantation (transplant eligible and ineligible patients)

Section: STUDY POPULATION

- Clarification that patients who are not liver transplant eligible or listed for liver transplantation will also be eligible for the study
- Modification of inclusion and exclusion criteria

Section: SECONDARY ANALYSES

- Clarification of the timepoint for those patients who were transplant ineligible or did not undergo a transplant.

General formatting and administrative clarifications were made throughout the protocol.

INFUSE: Summary of VERSION 3 Dated: March 30, 2021 Changes

Section: SYNOPSIS

- Clarification that patients who are liver transplant eligible with anticipation of being placed on the liver transplant wait list are eligible for the study
- Clarification of inclusion criterion to remove the restriction that eligible subjects are anticipated to be placed in the liver transplant wait list within 7 days of screening
- Clarification of total volume of 0.9% sodium chloride used for drug infusion

- Clarification that some lab assessments and procedures will only be collected if they are performed as per site's standard of care

Section: STUDY POPULATION

- Clarification that patients who are liver transplant eligible with anticipation of being placed on the liver transplant wait list are eligible for the study

Section: TERLIPRESSIN

- Update of stability and microbiology testing, including stability at refrigerated temperatures of 48 hours and room temperature for 24 hours
- Clarification of total volume of 0.9% sodium chloride used for drug infusion

Section: ASSESSMENTS AND PROCEDURES

- Clarification that assessments are completed per sites' Standard of Care.
- Clarification of the timepoints for echocardiogram
- Clarification of the timepoints for optional cystatin c and biomarker samples
- Clarification that optional biomarker samples may be drawn +/- 1 day of the target day
- Clarification that some lab assessments and procedures will only be collected if they are performed as per site's standard of care
- Clarification of acceptable window for follow up assessments

Section: STUDY ASSESSMENTS

- Clarification that some lab assessments and procedures will only be collected if they are performed as per site's standard of care

Section: DETAIL OF LABORATORY ASSESSMENTS AND PROCEDURES

- Clarification of the timepoints for optional cystatin c and biomarker samples
- Clarification that some lab assessments and procedures will only be collected if they are performed as per site's standard of care

Section: REFERENCES

- Addition of reference Bui 2020

Section: APPENDIX C

- Addition of Appendix C: Terlipressin Microbiology

General formatting and administrative clarifications were made throughout the protocol.

INFUSE: Summary of VERSION 2 Dated: September 15, 2020 Changes

Section: SYNOPSIS

- Added clarification for retrospective case collection time-period parameters.
- Exclusion criteria addition to exclude ACLF grade 3 subjects.
- Exclusion criteria addition to exclude subjects with SCr greater than 5.0 mg/dL unless approved by Sponsor Medical Monitor.
- Exclusion criteria clarification on participation in other clinical trials.
- Exclusion criteria clarification on prior use of vasopressors for prospective subjects.
- Dosing clarification that only 0.9% sodium chloride solution should be used.
- Lab clarification on collection of BUN and eGFR.

Section: INVESTIGATIONAL PLAN

- Added clarification for retrospective case collection time-period parameters.
- Exclusion criteria addition to exclude ACLF grade 3 subjects.
- Exclusion criteria addition to exclude subjects with SCr greater than 5.0 mg/dL unless approved by Sponsor Medical Monitor.
- Exclusion criteria clarification on participation in other clinical trials.
- Exclusion criteria clarification on prior use of vasopressors for prospective subjects.

Section: STUDY DRUG STORAGE AND PREP

- Corrected stability of study drug once reconstituted is 48 hours for this study.

Section: ADMINISTRATION

- Clarification on dosing procedures.

Section: SCHEDULE OF ASSESSMENTS

- Clarifications on assessments to be collected

Section: PHYSICAL EXAMINATION

- Added collection of Estimated Dry Body Weight.

Section: ECHOCARDIOGRAM

- Clarification on collection requirements.

Section: VITAL SIGNS

- Clarification of vital sign collection parameters.

Section: ADVERSE EVENTS

- Clarification that SAEs are collected through 30 days post treatment. Deaths are reported until study completion but will not be SAEs if occurred after SAE reporting timeframe.

Section: SERUM ELECTROLYTES & BIOCHEMISTRY

- Clarification of assessments to be collected.

Section: HEMATOLOGY

- Clarification of assessments to be collected.

Section: SERIOUS ADVERSE EVENTS

- Clarification on reporting requirements
- Deletion of Adverse Event information due to not applicable for protocol.
- Clarification on SUSAR reporting.

Section: COLLECTION OF ADVERSE EVENTS/SERIOUS OR UNEXPECTED

- Clarification of reporting procedures.

Section: SITE REPORTING TO SPONSOR

- Correction to reporting contact information.

Section: SAFETY VARIABLES

- Clarification of death collection.

Section: STUDY AND STUDY SITE DISCONTINUATION CRITERIA

- Removal of incorrect Sponsor reference.

Section: REFERENCES

- Added a protocol reference for Electrocardiogram/Echocardiogram assessments.

General formatting and administrative clarifications were made to overall Protocol

1 SYNOPSIS

(synopsis to follow)

SYNOPSIS
Name of Sponsor/Company: University of Pennsylvania
Name of Investigational Product: Terlipressin
Name of Active Ingredient: Terlipressin
Title of Study: A Multi-Center, Open Label, Collaborative Research Study to Treat HRS-AKI Patients with Continuous Terlipressin Infusion
Study Centers: Approximately 5-10 sites in the United States of America
Phase of Development: Phase 3
Objectives: Primary: To assess safety/efficacy for continuous terlipressin infusion in adult subjects with Hepatorenal syndrome- Acute Kidney Injury (HRS-AKI) who are in one of two groups: 
1. On the liver transplant wait list or liver transplant eligible with anticipation of being placed on the liver transplant wait list2. Not eligible for liver transplant (limited to 25 patients)
Methodology: Prospective Terlipressin Group - Patients to be treated with open label terlipressin by infusion following an initial bolus dose of 0.5mg. Retrospective Control Group – Historical patients who would have met inclusion/exclusion criteria detailed below and received at least 48 hours of treatment for HRS-AKI according to center's standard-of-care (Midodrine/Octreotide (M&O), albumin, or other vasopressor)
Number of Subjects (Planned): Prospective Terlipressin Group - approximately 50 terlipressin treated subjects Retrospective Control Group - approximately 15-25 subjects per clinical site that were treated for HRS-AKI, that would have met the inclusion/exclusion criteria below as well as having critical clinical data points to enable a comparison of the Prospective and Retrospective groups. Retrospective cases collected from each site should include eligible patients starting from prior to site IRB approval for this protocol and going back

Collaborative Research Study, Version 4: 06/29/21
To Treat HRS-AKI Patients with Continuous Terlipressin Infusion

to January 2015. Subjects enrolled in a blinded clinical trial in this time period are excluded.

Diagnosis and Main Inclusion/Exclusion Criteria:

Adult subjects that are listed for liver transplant or liver transplant eligible with anticipation of being placed on the liver transplant wait list and have a diagnosis of HRS-AKI based on 2015 revised International Ascites Club (IAC) diagnostic criteria.

Inclusion Criteria:

1. Written informed consent by subject or legally authorized representative.
2. At least 18 years of age.
3. Cirrhosis and ascites.
4. No sustained improvement in renal function (less than 20% decrease in SCr) at least 48 hours after diuretic withdrawal and after plasma volume expansion with albumin (given daily for two days - 48 hours minimum from 1st dose). If SCr improves by \geq 20 % but plateaus (\leq 10 % fluctuation in sCr) and remains above 1.5 mg/dl for \geq another 48 hrs and there are no features of acute tubular necrosis.
5. Increase in SCr by at least \geq 0.3 mg/dl OR 1.5-2 fold above baseline (AKI stage 1 and above), to a SCr of \geq 1.5 mg/dl at the time of initiating treatment. Baseline SCr is defined as the most recent, lowest SCr within last 6 months before date of current admission.
6. A.) On liver transplant wait list or liver transplant eligible with anticipation of being placed on the liver transplant wait list. B.) Patients not on the transplant waitlist or transplant eligible are also eligible for the trial (maximum 25 subjects)

Exclusion Criteria:

1. Serum creatinine level greater than 5.0 mg/dL. Subjects with value greater than 5.0 mg/dL may be enrolled with Sponsor prior approval.
2. MELD score of \geq 35
3. Acute on Chronic Liver Failure (ACLF) grade 3 (according to the CLIF Consortium grading system)
4. Uncontrolled sepsis and/or uncontrolled bacterial infection (e.g., persisting bacteremia, persisting ascitic fluid leukocytosis, fever, increasing leukocytosis with vasomotor instability).
5. Shock.
6. Current or recent (within 4 weeks) treatment with or exposure to nephrotoxic agents: e.g., aminoglycosides, amphotericin, cyclosporine A, cisplatin, nonsteroidal anti-inflammatory drugs (NSAIDs: e.g., ibuprofen, naproxen, diclofenac), significant exposure to radiographic contrast agents (large doses or multiple injections of iodinated contrast media; e.g., during coronary or abdominal angiogram).

Collaborative Research Study, Version 4: 06/29/21
To Treat HRS-AKI Patients with Continuous Terlipressin Infusion

7. Estimated life expectancy of less than 7 days.
8. Advanced hepatocellular Carcinoma with expected life expectancy of < 6 months
9. Superimposed acute liver injury due to drugs (e.g., acetaminophen), dietary supplements, herbal preparations, viral hepatitis, or toxins (e.g., Amanita toxin with mushroom poisoning carbon tetrachloride), with the exception of acute alcoholic hepatitis.
10. Evidence of obstructive uropathy or parenchymal renal disease. Renal ultrasound or other imaging not required but should be taken if suspicious.
11. Tubular epithelial casts, heme granular casts (range of 1-3 granular casts acceptable), hematuria or microhematuria on urinalysis that is indicative of acute tubular necrosis and/or intrinsic renal disease.
12. Subjects known to be pregnant; all women of child-bearing age and potential must have a negative pregnancy test.
13. Severe cardiovascular disease, including, but not limited to, unstable angina, pulmonary edema, congestive heart failure, or persisting symptomatic peripheral vascular disease, myocardial infarction or stable chronic angina within the past 12 months, or any other cardiovascular disease judged by the investigator to be severe and creates a risk to subject with concurrent terlipressin use.
14. Current or recent (within 4 weeks) renal replacement therapy (RRT) or anticipation of RRT within 3 days on enrollment.
15. Participation in other clinical research involving investigational medicinal products within 30 days of starting study drug that would adversely affect participation in this or the current trial.
16. Transjugular intrahepatic portosystemic shunt (TIPS) within 30 days of starting study drug.
17. For the Prospective Group: All vasopressors must be stopped prior to treatment with terlipressin. Use of vasopressors (e.g., norepinephrine, epinephrine or vasopressin dopamine or other vasopressors) of ≥ 3 consecutive days within the prior 14-day screening period are excluded. Patients receiving a vasopressor other than midodrine within 24 hours of qualifying SCr are excluded, i.e., a 24-h washout is required prior to enrollment.
Note: Patients receiving midodrine and octreotide may be enrolled. Midodrine and octreotide treatment must be stopped prior to enrollment.
18. Known allergy or sensitivity to terlipressin.

Investigational Product, Dosage and Mode of Administration:

Prospective Terlipressin Group:

Collaborative Research Study, Version 4: 06/29/21
To Treat HRS-AKI Patients with Continuous Terlipressin Infusion

Terlipressin will be administered intravenously as a bolus injection for the first dose, then by continuous IV infusion.

Retrospective Control Group:

Dose and method of administration for M&O, albumin, or other vasopressor

Dosage and Mode of Administration:

For Retrospective Control Group:

Dosing for M&O, albumin, or other vasopressor will be reported as it was recorded on the subject's chart.

For Prospective Terlipressin Group:

Terlipressin will be supplied in single-use, sterile 6-mL vials containing 1 mg of lyophilized Terlipressin acetate (equivalent to 0.85 mg Terlipressin free base) with 10 mg mannitol as a bulking agent/stabilizer.

Initial Dosing:

Terlipressin will be administered intravenously as a bolus injection (the vial will be reconstituted with 5 mL of sterile 0.9% sodium chloride solution and given over 1 minute at a dose of 0.5 mg).

- Continued dosing will be by 2 mg infusion per day. For continuous infusion, the dose of terlipressin is to be dissolved in 0.9% sodium chloride solution and infused with a pump.

Dose Modifications:

- If on Day 3 the SCr is not 30% lower from the baseline value, increase infusion dose to 4 mg per day.
- If on Day 5 the SCr is not 50% lower from the baseline value, increase infusion dose to 6-8 mg per day, per PI discretion. Dosing can be increased by more than 1 mg increment at Day 5 or beyond, up to a maximum of 8 mg/day.
- If the subject has infusion stopped for \geq 4 hours, a 0.5 mg bolus should be given prior to restarting infusion.
- The drug should not be used in subjects with severe coronary artery disease or in the setting of circulatory overload, pulmonary edema, or bronchospasm as determined by the Investigator. If drug therapy has been initiated, Investigator can also decide not to increase the dose, based on the patient's status with regard to the above, based on individual subject condition.

Collaborative Research Study, Version 4: 06/29/21
To Treat HRS-AKI Patients with Continuous Terlipressin Infusion

- If dosing is interrupted due to an adverse event, terlipressin may be re-started, at the discretion of the investigator, at the same or lower dose as per protocol. Terlipressin will not be restarted if dosing was interrupted due to cardiac ischemia or mesenteric ischemia.

Treatment Discontinuation:

- Terlipressin may be continued until 24 hours after serum creatinine has reached the lowest value possible as determined by Principal Investigator, up to a maximum of 14 days.
- After a minimum of 72 hours post final dose escalation and tolerability, if the SCr is at or above enrollment value, terlipressin should be discontinued.
- If 72 hours after final dose escalation, there is no further improvement in SCr, continuation of terlipressin is at the discretion of the Principal Investigator at the clinical site.
- If a subject is initiated on RRT, terlipressin can be continued for a maximum of 72 hours after initiation of RRT.
- Terlipressin must be discontinued when the subject is to undergo liver transplantation, TIPS, or any other vasopressor therapy (single administration of vasopressor for cardiac stress test is acceptable)
- Dosing must be permanently discontinued if an event of cardiac ischemia or mesenteric ischemia occurs.

Retreatment:

If judged by the investigator to be potentially beneficial, subjects who demonstrate at least a partial response during the initial treatment course (at least 50% reduction in SCr) and develop recurrence of HRS-AKI may be retreated for a maximum of 14 days. To qualify for retreatment the subject must again meet the study inclusion/exclusion criteria. Retreatment may occur within 90 days of the subject's first dose of terlipressin.

Duration of Treatment:

For the Prospective Terlipressin Group, the active treatment period will be up to 14 days, allowing 1 retreatment cycle.

For both Prospective and Retrospective Subjects:

All subjects will be followed:

Post treatment clinical data collection will be through phone call and chart review. Creatinine, BUN and eGFR will be recorded per standard of care, recording mortality and the date of last dialysis (CVVH or HD) session for the following time points:

Collaborative Research Study, Version 4: 06/29/21
To Treat HRS-AKI Patients with Continuous Terlipressin Infusion

Day 7 +/- 2 days;
Day 14 +/- 3 days;
Day 30 +/- 1 week and
Day 90 +/- 1 week
Day 180 +/- 2 weeks and
Day 365 +/- 2 weeks.

For subjects who have a liver transplant Post Treatment

If the subject has a liver transplant recorded prior to the 90-Day visit (phone call or chart review), additional follow up will occur through one year after liver transplant.

Creatinine, BUN and eGFR will be recorded per standard of care, recording mortality and the date of last dialysis (CVVH or HD) session for the following time points:

Day 0 (date of transplant) – record allocation MELD and last calculated MELD prior to transplant;
Day 7 +/- 2 days;
Day 14 +/- 3 days;
Day 30 +/- 1 week,
Day 90 +/- 1 week,
Day 180 +/- 2 weeks and
Day 365 +/- 2 weeks.

Key Efficacy and Safety Data Assessment:

Primary Efficacy Assessment:

Improvement of renal function (SCr) from Day 1 through end of treatment, repeated measure analysis. SCr will be collected at baseline and daily from Day 1 through end of treatment.

Secondary Efficacy Endpoints:

- Improvement of renal function (SCr) from Day 1 through end of treatment, repeated measure analysis as compared to the Retrospective Control Group.

Collaborative Research Study, Version 4: 06/29/21
To Treat HRS-AKI Patients with Continuous Terlipressin Infusion

- For the Prospective Terlipressin Group alone and also in comparison to the Retrospective Control Group:
 - Incidence of dialysis by Day 30 and Day 90 of follow up.
 - Survival by Day 30 and Day 90 follow up.
 - Transplant by Day 30 and Day 90 follow up.
 - Serum creatinine at Day 30 and Day 90 follow up
 - Serum creatinine and incidence of dialysis at Day 30, Day 90, Day 180, and Day 365 after liver transplantation
 - Incidence of kidney transplant within one year after liver transplant
 - Descriptive analysis of number of simultaneous liver kidney transplants and episodes of graft rejection by Day 90 and Day 365 after liver transplant

Safety:

Safety review and assessments will be made only for the Prospective Terlipressin Group and will include the following:

- Serious adverse events up to 30 days after end of treatment.

Statistical Methods:

A formal sample size calculation is not applicable for this study. It is expected that at least 50 subjects across more than 5-10 institutions may receive terlipressin treatment during the course of the research study.

Additionally, up to 150 subjects across all clinical sites will have their Retrospective data collected. Descriptive analysis will be planned for the efficacy and safety data collected. Sponsor may perform additional analysis not specified in study protocol.

Contents

1	SYNOPSIS	10
2	LIST OF ABBREVIATIONS	22
3	INTRODUCTION	24
3.1	HEPATORENAL SYNDROME	24
3.2	TERLIPRESSIN	25
3.3	EFFICACY	25
3.4	SAFETY	26
3.5	RETROSPECTIVE CONTROL GROUP: M&O TREATED SUBJECTS	26
3.5.1	MIDODRINE AND OCTREOTIDE	26
3.5.2	M&O OFF-LABEL USE	26
4	STUDY RATIONALE	27
5	SAFETY AND EFFICACY ASSESSMENTS	27
5.1	EFFICACY VARIABLES	27
6	INVESTIGATIONAL PLAN	28
6.1	OVERALL STUDY DESIGN AND PLAN: DESCRIPTION	28
7	STUDY POPULATION	29
7.1	POPULATION RATIONALE	29
7.2	NUMBER OF SUBJECTS TO BE STUDIED	29
7.3	INCLUSION/EXCLUSION CRITERIA	29
7.4	SUBJECT WITHDRAWAL CRITERIA	31
7.5	PROTOCOL DEVIATIONS	31

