6. Current or recent (within 4 weeks) treatment with or exposure to nephrotoxic agents: e.g., aminoglycosides, amphotericin, cyclosporine A, cisplatin, nonsteroidal anti-inflammatory drugs (NSAIDs: e.g., ibuprofen, naproxen, diclofenac), significant exposure to radiographic contrast agents (large doses or multiple injections of iodinated contrast media; e.g., during coronary or abdominal angiogram).
7. Estimated life expectancy of less than 7 days.
8. Advanced Hepatocellular Carcinoma (HCC) with expected survival of < 6 months.
9. Superimposed acute liver injury due to drugs (e.g., acetaminophen), dietary supplements, herbal preparations, viral hepatitis, or toxins (e.g., *Amanita* toxin with mushroom poisoning carbon tetrachloride), with the exception of acute alcoholic hepatitis.
10. Evidence of obstructive uropathy or parenchymal renal disease. Renal ultrasound or other imaging not required but should be taken if suspicious.

Collaborative Research Study, Version 4: 06/29/21
To Treat HRS-AKI Patients with Continuous Terlipressin Infusion

11. Tubular epithelial casts, heme granular casts (range of 1-3 granular casts acceptable), hematuria or microhematuria on urinalysis that is indicative of acute tubular necrosis and/or intrinsic renal disease.
12. Subjects known to be pregnant; all women of child-bearing age and potential must have a negative pregnancy test.
13. Severe cardiovascular disease, including, but not limited to, unstable angina, pulmonary edema, congestive heart failure, or persisting symptomatic peripheral vascular disease, myocardial infarction or stable chronic angina within the past 12 months, or any other cardiovascular disease judged by the investigator to be severe and creates a risk to subject with concurrent terlipressin use.
14. Current or recent (within 4 weeks) renal replacement therapy (RRT) or anticipation of RRT within 3 days on enrollment.
15. Participation in other clinical research involving investigational medicinal products within 30 days of starting study drug that would adversely affect participation in this or the current trial.
16. Transjugular intrahepatic portosystemic shunt (TIPS) within 30 days of starting study drug.

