15.3 Sample Size Considerations

A formal sample size calculation is not applicable for the proposed study. However, at least 50 subjects across more than 5-10 institutions may receive terlipressin treatment during the course of the intervention portion of the study. For the comparison of the terlipressin treatment group and retrospective controls, we expect to have 50 subjects in the intervention group and 150 subjects, assembled from the study sites, in the control group. Assuming a type 1 error of 0.05 and power of 80%, we expect to be able to detect a range of differences in serum creatinine (SCr) depending on the standard deviation of the change (primary endpoint) expected for the groups (see below). Based on results from the REVERSE trial, a change in SCr of as small as 0.05 mg/dL would be able to be detected if the standard deviation for the change approximated 0.10 mg/dL and a pre-specified sample size of 200 subjects, 50 of whom are in the intervention arm, is used for the calculation.

	Δ SCr mg/dL				
Detectable Difference	0.46	0.34	0.23	0.11	0.05
Standard Deviation	1.00	0.75	0.50	0.20	0.10

Given the relatively small number of subjects proposed for inclusion in this terlipressin study, we will likely be underpowered to detect a difference in the other secondary outcomes being explored.

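### The controls' blinded-trial exclusion is tied to a calendar window, not the index episode, so it can remove survivors and may bias the Day 30 and Day 90 survival comparison

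*Combined protocol and SAP*

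**What the plan says.** The Synopsis (Number of Subjects) sets the control sampling frame, with January 2015 as its earliest date: "Retrospective cases collected from each site should include eligible patients starting from prior to site IRB approval for this protocol and going back". The next sentence is the exclusion: "Subjects enrolled in a blinded clinical trial in this time period are excluded". Sections 6.1 and 7.2 repeat both. None of the three places links the exclusion to the HRS-AKI episode, to a type of trial, or to the date control treatment began.

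Controls must also be patients "that would have met the inclusion/exclusion criteria below", so the blinded-trial sentence comes on top of the common criteria. Those already contain a rule on trial participation, exclusion 15 in 7.3: "Participation in other clinical research involving investigational medicinal products within 30 days of starting study drug that would adversely affect participation". That rule is limited to 30 days around study drug and to participation that would interfere, and it covers investigational products whether blinded or not. No section removes a terlipressin subject for joining another trial afterwards.

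The between-group outcomes include "Survival by Day 30 and Day 90 follow up" and SCr to end of treatment, "repeated measure analysis as compared to the Retrospective Control Group". Both are listed as secondary.

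**The concern.** In a comparison with historical controls, eligibility should be settled by what is known when index treatment starts. The only period the exclusion can grammatically refer to is the case-collection window, which spans several years. A site that follows it literally would drop a patient treated for HRS-AKI in 2016 who recovered and entered a blinded trial in 2018. A patient who died in 2016 could not be dropped by that route. Control eligibility then depends partly on later events that require survival, and the terlipressin group has no matching condition.

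The Day 30 and Day 90 survival comparison is at stake. A larger control group would not cure selection on later events. Adjustment for baseline covariates would not in general cure it either, and section 15.1 describes adjustment only for the SCr model.

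**Working it through.** **Plan's own figure.** The documents give no survival figure, so the only design figure for the control comparison is the detectable SCr difference in 15.3. That section states: "we expect to have 50 subjects in the intervention group and 150 subjects, assembled from the study sites, in the control group". With two-sided alpha 0.05, power 80% and SD 1.00 mg/dL:

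(1.960 + 0.842) × 1.00 × √(1/50 + 1/150) = 2.802 × 0.1633 = 0.458 mg/dL, against 0.46 stated.

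This confirms the group sizes used below. The point does not depend on it.

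**Assumed inputs.** The documents give neither of these:
- S, true Day 90 survival in eligible controls: 40%, 50%, 60%.
- f, the share of those survivors removed for later blinded-trial entry: 5%, 10%, 20%.

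**Step 1: survivors only are removed.** Observed survival = S(1−f) / [S(1−f) + (1−S)].

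| S | f = 5% | f = 10% | f = 20% |
|---|---|---|---|
| 40% | 0.38/0.98 = 38.8% (−1.2) | 0.36/0.96 = 37.5% (−2.5) | 0.32/0.92 = 34.8% (−5.2) |
| 50% | 0.475/0.975 = 48.7% (−1.3) | 0.45/0.95 = 47.4% (−2.6) | 0.40/0.90 = 44.4% (−5.6) |
| 60% | 0.57/0.97 = 58.8% (−1.2) | 0.54/0.94 = 57.4% (−2.6) | 0.48/0.88 = 54.5% (−5.5) |

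Figures in brackets are the shift in percentage points.

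**Step 2: non-survivors are removed as well.** The same sentence removes patients enrolled before or during the episode, some of whom die. It also removes patients who enrol after the episode and die before Day 90. With a share g of non-survivors removed, observed survival = S(1−f) / [S(1−f) + (1−S)(1−g)]. At S = 50% and f = 10%:
- g = 5%: 0.45/0.925 = 48.6%, still low.
- g = 10%: 0.45/0.90 = 50.0%, no bias.
- g = 15%: 0.45/0.875 = 51.4%, bias reversed.

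The sign therefore depends on f against g, and the documents inform neither.

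**Step 3: effect on a test.** The plan names no test for survival. Assume an unadjusted two-proportion test at two-sided 5%, 50 against 150 retained controls, no true effect and g = 0. At S = 50% the rejection rate is about 6.2% for f = 10% and 10.5% for f = 20%. For S from 30% to 70% it is about 6% for f = 10% and 9 to 11% for f = 20%. For scale, the standard error of the difference at S = 60% is √[0.6 × 0.4 × (1/50 + 1/150)] = 0.08, or 8 points.

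**Step 4: on-treatment SCr.** The shift is the change in survivor share times the gap in mean SCr change between survivors and non-survivors. At S = 50% and f = 10% the change in share is 0.500 − 0.474 = 0.026. An assumed gap of 0.5 to 1.0 mg/dL gives 0.01 to 0.03 mg/dL, against a detectable difference of 0.46 at SD 1.00.

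**The case against.** The strongest reply is that the sentence was meant to exclude episodes managed inside a blinded trial. Control dosing is taken from the chart (8.4), and controls must have had at least 48 hours of standard-of-care treatment. A masked episode cannot be shown to qualify, so excluding it is sensible. That reading is possible and its aim should be kept. But the text does not say it, and 5 to 10 sites would have to guess.

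Second, f may be small. Sites collect 15 to 25 cases each, going back from IRB approval. If they work backwards, recent cases fill the quota and have had little time to enter another trial. This is fair, and the documents do not support 20% over 5%. At 5 to 10% the shift is 1.2 to 2.6 points against a standard error of about 8, and 15.3 already concedes low power for the other secondary outcomes. Low power does not excuse an avoidable bias, but it limits how much this one matters.

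A reader might infer three stronger conclusions, which the documents do not support:
- That survivors are in fact removed and terlipressin is favoured. Step 2 shows that the net effect could be zero or reversed.
- That Day 365 outcomes suffer more. Survival is compared only at Days 30 and 90. The Day 365 outcomes concern transplanted patients or those alive without transplant, and removing survivors need not shift SCr or dialysis among survivors.
- That controls given open-label terlipressin enter as recipients of another vasopressor. All sites are in the US, where sections 3.1 and 3.5.2 describe no approved therapy and terlipressin as unavailable. Nothing suggests such controls exist.

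**Conclusion.** The concern holds as a defect in the eligibility wording. The exclusion is anchored to the calendar window, applies to controls only and, followed literally, selects on events after index treatment. It can remove control survivors and may bias the Day 30 and Day 90 survival comparison towards terlipressin. If only survivors are removed, the understatement of control survival is about 1.2 to 5.6 points over S = 40 to 60% and f = 5 to 20%. These ranges are assumptions, and the documents fix neither the net sign nor the size. The primary efficacy variable, on-treatment SCr, is probably little affected. The change is worth making because the problem is avoidable at almost no cost, not because a large bias has been shown.

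**What to change.** In the Synopsis, 6.1 and 7.2, replace the sentence with wording such as:

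*In addition to exclusion 15, applied relative to the start of index HRS-AKI treatment, controls who were enrolled in a blinded trial of an investigational product during the index HRS-AKI episode or within 30 days before index treatment are excluded. Trial enrolment after the index episode does not exclude a control, is recorded, and is handled the same way in both groups.*

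The new rule must be added to exclusion 15 and not replace it, because exclusion 15 already applies to controls and also covers unblinded products. State when the index episode ends, and report the number of controls excluded under this rule per site.

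The cost is one sentence in three places and one date check per chart. A few controls may receive a blinded product later in follow-up, as terlipressin subjects also may. Enrolment during the episode but after index treatment has started would still exclude a control. That leaves a small residual selection, accepted because treatment in such cases is masked.
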